5 STATISTICAL ANALYSES

5.1 General considerations

All tables, figures and listings (TFLs), including statistical evaluation, will be produced by Parexel using SAS version 9.4 or higher (SAS Institute, Cary, North Carolina, USA) unless stated otherwise. The analyses covered in Section 5.3.1.4.1 and Section 5.3.2.1.4 will be produced by UCB. Analysis data will adhere to Clinical Data Interchange Standards Consortium (CDISC) guidance documents for Analysis Data Model (ADaM) and follow the UCB interpretation.

TFLs will be presented by treatment group and visit as applicable. Listings of all documented and calculated data will be presented by treatment group, study participant and visit. Data collected at unscheduled visits will be included in listings but not in any summary tables unless explicitly stated otherwise.

Continuous variables

Unless stated otherwise, summary statistics will be presented for continuous variables including number of participants (n), mean, standard deviation (SD), median, minimum and maximum. When summarizing efficacy endpoints, the inter quartile range (IQR) will also be included. Geometric mean, geometric coefficient of variation (CV) and 95% CI for the geometric mean will also be presented in the summaries of UCB5099 and N-oxide metabolite concentration data. Further details on presenting concentration data will be given in Section 5.5.1.

Generally, means (arithmetic or geometric), standard deviations, medians and IQRs will use one decimal place more than the original data and confidence intervals will use 1 decimal place more than the value which they are constructed around. Depending on the data format this could be significant figures rather than decimal places. Minimum and maximum will use the same format as the original data. In listings, if the data is coming directly from the CRF it should be presented exactly as captured. For derived variables, data should be reported using 1 decimal place more than the values which they are calculated from.

For all continuous efficacy endpoints, summary statistics will be produced for both observed results and changes from Baseline.

Time to event variables

For time-to-event variables, descriptive summary tables will include the number and percentage of study participants who reach the endpoint by each visit.

Categorical variables

Categorical variables will be summarized using frequency counts and percentages. Unless otherwise stated, the denominator for the percentage calculations will be based on the number of study participants in the respective analysis set, treatment group and visit (as applicable) with non-missing data.

Unless otherwise noted, all percentages will be displayed to 1 decimal place. No percentage will be displayed for zero counts, and no decimal will be presented when the percentage is 100%.

Estimands

Estimands will be described as a function of their attributes: (1) the population of interest, (2) the treatment effect of interest, (3) the participant-level variable (or endpoint) of interest, (4) the specification of how ICEs are reflected in the scientific question of interest, and (5) the population-level summary for the variable/endpoint. (See [Table 1-1](#), [Table 1-2](#) and [Table 1-3](#) for the estimands and ICE handling strategies to be used in this study)

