v First day of UCB0599 administration will be the evening of the RL Visit (Day 0); last administration will be in the morning of the EOT Visit (Day 540).

w Visit 8a will be conducted as an unscheduled visit.

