As a result of these clinical data, drug hypersensitivity is now considered an important identified risk by the Sponsor and, therefore, further measures of risk monitoring and minimization are included. Sites will be informed and trained appropriately about the risk of a hypersensitivity reaction (such as rash, angioedema, or anaphylaxis) and the actions that need to be taken in case of hypersensitivity reaction. The participant will be informed by the Investigator during the consent procedure about the risk of a hypersensitivity reaction (such as rash, angioedema, or anaphylaxis) and other important potential risks for UCB0599. Risk mitigation measures include using a standard approach of (1) obtaining a detailed history of the hypersensitivity reaction and its evolution, (2) response with appropriate treatment, if needed, (3) a detailed physical examination, regular monitoring of vital signs, and (4) the addition of a guidance for the evaluation of suspected hypersensitivity reactions (please refer to Section 8.3.6.1) and reporting of the suspected hypersensitivity reaction as an adverse event of special interest (AESI).

To monitor the potential risk of hepatotoxicity, monthly routine liver function tests are mandated during the first 6 months of treatment for study participants who receive multiple doses of study medication (see Schedule of Activities, Section 1.3). In addition, any cases meeting Hy's law criteria must be reported as an AESI. Sites will be informed and trained appropriately.

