**Table 10-1: Phase 2 Liver Chemistry Stopping Criteria and Follow-up Assessments**

Liver Chemistry Stopping Criteria	

 
Monitor the participant until liver chemistry test abnormalities resolve, stabilize, or return to Baseline (see MONITORING).
 
Do not restart/rechallenge participant with study medication unless allowed per protocol and Sponsor approval is granted
 
If restart/rechallenge not allowed per protocol or not granted, permanently discontinue study medication and continue participant in the study for any protocol specified follow up assessments
 
Consider the need for a toxicology Screening
 
 
MONITORING:
 
If <math>\text{ALT} \geq 3 \times \text{ULN}</math> AND bilirubin <math>\geq 2 \times \text{ULN}</math> or INR <math>> 1.5</math>:
 
 
Repeat liver chemistry tests (include ALT, aspartate transaminase [AST], alkaline phosphatase, bilirubin) and perform liver event follow-up assessments within 24 hours.
 
Monitor participant twice weekly until liver chemistry test abnormalities resolve, stabilize, or return to Baseline.
 
A specialist or hepatology consultation is recommended.
 
 
If <math>\text{ALT} \geq 3 \times \text{ULN}</math> AND bilirubin <math>< 2 \times \text{ULN}</math> and INR <math>\leq 1.5</math>:
 
 
Repeat liver chemistry tests (include ALT, AST, alkaline phosphatase, bilirubin) and perform liver chemistry follow up assessments within 24 to 72 hours.
 
Monitor participants weekly until liver chemistry abnormalities resolve, stabilize, or return to Baseline.
 
	
 
Serum creatine phosphokinase (CPK), lactate dehydrogenase (LDH), and (optional) gamma-glutamyl transferase (GGT)
 
Fractionate bilirubin, if total bilirubin <math>\geq 2 \times \text{ULN}</math>
 
Obtain complete blood count with differential to assess eosinophilia
 
Record the appearance or worsening of clinical symptoms of liver injury (eg, fatigue, nausea, vomiting, right upper quadrant pain), or hypersensitivity, on the adverse event (AE) report form
 
Record use of concomitant medications (including acetaminophen, herbal remedies, and other over-the-counter medications) on the concomitant medications CRF
 
Record alcohol use on the liver event alcohol intake CRF
 
Exclude pregnancy
 
 
If <math>\text{ALT} \geq 3 \times \text{ULN}</math> AND bilirubin <math>\geq 2 \times \text{ULN}</math> or INR <math>> 1.5</math>:
 
 
Anti-nuclear antibody, anti-smooth muscle antibody, Type 1 anti-liver kidney microsomal antibodies, and quantitative total immunoglobulin G (IgG) or gamma globulins
 
Serum acetaminophen (EAN paracetamol)
 
Liver imaging (ultrasound, magnetic resonance, or computerized tomography) and/or liver biopsy to evaluate liver disease; complete liver
 

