### 10.11.1 Amendment 5 (30 Jun 2023)

#### Overall Rationale for the Amendment

PD0053 Protocol Amendment 5 was enacted to incorporate additional laboratory tests at Day 150 in order to allow for close monitoring of liver function test parameters.

This amendment is considered to be substantial based on the criteria set forth in Article 10(a) of Directive 2001/20/EC of the European Parliament and the Council of the European Union.

The following changes were implemented:

Section # and Name	Description of Change	Brief Rationale
Section 1.2 Schema	An in-clinic visit at Day 150 (Month 5) (Visit 8a) was added.	To increase the monitoring of liver function test parameters.
Section 2.3 Benefit/Risk assessment	Text was updated to delete hematological, gastrointestinal, and musculoskeletal effects from the list of potential risks, to clarify that the potential risk of hepatotoxicity is based on clinical data, to clarify that renal laboratory abnormalities are kept under close safety monitoring, and to clarify the measures to mitigate the potential risk of hepatotoxicity.	To align with the warnings and precautions provided in the updated Section 6.3.4 of the Investigator's Brochure.
Section 8 Study assessments and procedures	The maximum blood volume collected from each participant during the study was updated to 510mL.	To account for the blood sampling at the added study visit.
Section 8.3 Adverse events and serious adverse events	Text was updated to add that for results disclosure on public registries, TEAEs and treatment-emergent SAEs will be published.	To clarify the disclosure of TEAEs and treatment-emergent SAEs.
Section 10.11 Appendix 11: Protocol Amendment History	The Protocol Amendment Summary of Changes Table for the previous amendment has been added.	Minor administrative change.
Throughout	Minor editorial and document formatting revisions.	Minor, therefore have not been summarized.

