5.4.3 Additional safety assessments

5.4.3.1 Clinical safety laboratory assessments

Hematology, clinical chemistry, coagulation and urinalysis parameters will be assessed, see table 5.3 below for a full list of which parameters will be analyzed. Other screening and laboratory tests to be carried out are also covered in this table. The schedule of activities (protocol section 1.3) gives details on when these assessments are performed.

Hematology, clinical chemistry and coagulation laboratory results that were performed locally should be included in laboratory listings but not in summary tables and figures. Laboratory re-test results will be used in summary tables only if the original scheduled test result is not available, if the original result is available re-tests will be treated as unscheduled.

Table 5–3: Clinical laboratory assessments

Laboratory Assessments	Parameters					
Hematology	Platelet Count		RBC Indices: MCV MCH %Reticulocytes	WBC Count with Differential: Neutrophils ^b Lymphocytes ^b Monocytes Eosinophils ^b Basophils ^b		
	RBC Count ^b					
	Hemoglobin ^b					
	Hematocrit					
Clinical Chemistry	Blood Urea Nitrogen (BUN)	Potassium	Aspartate Aminotransferase (AST)/ Serum Glutamic-Oxaloacetic Transaminase (SGOT) ^b	Total and direct bilirubin		
	Creatinine	Sodium	Alanine Aminotransferase (ALT)/ Serum Glutamic-Pyruvic Transaminase (SGPT) ^b			
	Glucose (fasting at Screening and nonfasting at any visit thereafter)	Calcium	Alkaline phosphatase ^b			
Coagulation	International normalized ratio	Prothrombin time ^b	aPTT	Fibrinogen		
Routine Urinalysis	
 • Specific gravity • pH, glucose, protein, blood, ketones, bilirubin, urobilinogen, nitrite, leukocytes by dipstick • Microscopic examination (if blood or protein is abnormal) 					
Other Screening Tests	
 • Follicle-stimulating hormone and estradiol (as needed in women of non-childbearing potential only) • Immunoglobulin E • HbA1c (as needed in study participants with type 2 diabetes mellitus) • Urine drug screen (to include at minimum: amphetamines, barbiturates, cocaine, opiates, cannabinoids, methadone, and benzodiazepines) • Urine alcohol test • Serum and urine human chorionic gonadotropin (hCG) pregnancy test (as needed for women of childbearing potential)^a 					

Table 5–3: Clinical laboratory assessments

Laboratory Assessments	Parameters

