5.4.3.1.1 Laboratory values over time

Laboratory variables will be grouped according to the laboratory function panel and categorized as normal, high or low, if applicable, based on the reference range supplied by the analytical laboratory.

For urinalysis, hematology, coagulation and clinical chemistry observed results and changes from Baseline for numeric variables at each post-Baseline visit will be listed by treatment group, study participant and visit. Listings will flag values that fall outside of the normal range, and will include the reference ranges. Additionally, values that fall outside the reference ranges will be listed separately.

Clinical chemistry and hematology variables will be summarized descriptively by treatment group at each visit, for both observed values and changes from Baseline. These descriptive statistics will only be calculated if at most one third of the individual data points at any visit are missing or not quantifiable. If 3 or less participants have data available at any visit, only n, minimum and maximum will be presented. Plots of mean and mean change from Baseline will be presented by treatment group for all hematology and clinical chemistry laboratory variables. These plots will include all treatment groups overlaid on the same plot and will include error bars based on the SD (ie, mean \pm SD).

Measurements that are below the limit of quantification (BLQ) or above the limit of quantification (ALQ) will be presented as BLQ and ALQ in the listings. For the purpose of calculating change from Baseline or for descriptive statistics, BLQ values will be imputed with half of the lower limit of quantification (LLOQ) and ALQ values will be imputed to the upper quantification limit (if applicable).

A separate listing will be produced for study participants with Elevated Liver Function Results. Elevated results are defined as results meeting the following criteria:

- ALT or AST $\geq 3x$ (ULN)
- ALP $\geq 1.5x$ ULN
- Total bilirubin $\geq 1.5x$ ULN

The listing will display all scheduled and unscheduled visit data for participants who meet at least one of the above criteria was fulfilled. A summary of study participants who meet the criteria for potential drug-induced liver injury (PDILI) will be presented and a figure presenting liver function results over time for participants who meet the potential Hy's Law Criteria will be produced (this figure will only be produced if there are participants who meet the criteria).

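### No exception lets unscheduled, re-test or local results into the laboratory-based liver tables, so the Month 5 visit and off-schedule follow-up draws do not count there

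*SAP*

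**What the plan says.** **Default rule.** SAP 5.1 states: "Data collected at unscheduled visits will be included in listings but not in any summary tables unless explicitly stated otherwise". It names summary tables and does not mention figures.

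**Re-tests and local results.** SAP 5.4.3.1 states: "Laboratory re-test results will be used in summary tables only if the original scheduled test result is not available"; otherwise a re-test is handled as unscheduled. For local laboratories: "Hematology, clinical chemistry and coagulation laboratory results that were performed locally should be included in laboratory listings but not in summary tables and figures".

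**Month 5 visit.** Protocol 2.3 says that "monthly routine liver function tests are mandated during the first 6 months of treatment". The Amendment 5 rationale (Protocol 10.11.1) explains that the amendment brought in "additional laboratory tests at Day 150 in order to allow for close monitoring of liver function test parameters". Footnote w of the Schedule of Activities (Protocol 1.3) then says: "Visit 8a will be conducted as an unscheduled visit". The SAP is based on protocol amendment 6 but does not mention Visit 8a.

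**Liver follow-up.** Protocol Table 10-1 requires repeat testing once ALT reaches 3×ULN. Where bilirubin is also ≥2×ULN or INR is >1.5, it says: "Monitor participant twice weekly until liver chemistry test abnormalities resolve, stabilize, or return to Baseline". In the milder case monitoring is weekly.

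**Liver outputs.** SAP 5.4.3.1.1 plans a listing of elevated liver results, a PDILI summary, an elevated liver test table and several figures. SAP 6.1.6 adds a Hy's Law table with adjudication. Only the listing carries an exception: "The listing will display all scheduled and unscheduled visit data for participants who meet at least one of the above criteria".

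**The concern.** Hepatotoxicity is a named potential risk in Protocol 2.3, based on clinical data, and Visit 8a was added to watch for it. Followed literally, the SAP keeps that visit out of the tables that count participants crossing liver thresholds. It also keeps out the repeat draws at which a transaminase rise may be confirmed or joined by raised bilirubin.

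The effect on a threshold count runs one way. Leaving results out can lower the number of participants who meet a criterion or leave it unchanged, but cannot raise it. A reader comparing arms in the PDILI, elevated liver test or Hy's Law laboratory tables would not see that these results had been left out.

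The amendment dates suggest an unnoticed interaction. The handling of unscheduled data entered the SAP with SAP Amendment 1 (January 2023). Visit 8a came with Protocol Amendment 5 (June 2023).

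**Working it through.** The documents give no figure to reproduce. The check sets the inclusion rules against each liver output and counts visits from the Schedule of Activities.

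**Step 1: which results the rules remove**

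| Result | Laboratory summary tables | Figures | Elevated-liver listing |
|---|---|---|---|
| Scheduled, central | in | in | in |
| Visit 8a, central | out by default | not barred, source unstated | in |
| Off-schedule follow-up, central | out by default | not barred, source unstated | in |
| Re-test, original available | out by default | not barred, source unstated | in |
| Re-test, original unavailable | in | not barred, source unstated | in |
| Local laboratory | out | out | in |

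The listing column applies to participants who meet at least one of its criteria.

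**Step 2: whether any liver table overrides the default.** The PDILI summary, the elevated liver test table and the Hy's Law table say nothing about unscheduled data. The SAP does write such exceptions elsewhere. The Full Analysis Set definition (SAP 4) counts unscheduled assessments, and the elevated-liver listing shows them. A programmer would reasonably take silence to mean that the default applies.

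**Step 3: visits lost**
- Monthly draws from Month 1 to Month 6 are V5, V6, V7, V8, V8a and V9, which makes 6. Without V8a, 5 of 6 are tabulated.
- On-treatment post-baseline chemistry draws from V4 to V15, with V8a, number 13. V8a is 1/13 = 7.7%.
- The largest tabulated gap in the first six months becomes 180 − 120 = 60 days, against 30 days with Day 150.

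**Step 4: who can drop out.** SAP 5.4.3.1.1 describes the PDILI criterion as ALT or AST ≥3×ULN. If a scheduled central draw first crosses it, the participant is already counted and omitting later draws changes nothing. Two groups remain:
- participants whose only ALT or AST ≥3×ULN is on an excluded draw;
- participants whose bilirubin first reaches 2×ULN on an excluded draw, for the combined criterion.

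**Step 5: sensitivity for the Day 120 to 180 gap.** Assume that an excursion above threshold lasts d days, that its onset is uniform over the gap, that nominal visit days are kept, and that the participant has a Visit 8a. Capture is min(1, d/60) without Day 150 and min(1, d/30) with it.

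| d (assumed) | Without Day 150 | With Day 150 |
|---|---|---|
| 14 days | 14/60 = 23% | 14/30 = 47% |
| 28 days | 28/60 = 47% | 28/30 = 93% |
| 42 days | 42/60 = 70% | 100% |
| ≥60 days | 100% | 100% |

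The documents give neither a duration nor a rate of elevation, so these percentages do not convert into a number of participants.

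**The case against.** The strongest reply is that a serious liver case will be seen whatever these tables show. Potential Hy's Law is an adverse event of special interest (AESI) reportable within 24 hours, and Table 10-1 requires such cases to be reported as serious. AESI tables use the investigator's flag (SAP 5.4.2.1), and hepatic events are tabulated by a standardised MedDRA query (SAP 6.1.6). None of these depends on the visit label of a laboratory record. This stands. A reader might infer that reported liver cases vanish from every hepatotoxicity count, and the documents do not support that. The reply does not cover everything, however. An isolated ALT or AST ≥3×ULN does not meet the hepatic AESI definition. Its appearance as an adverse event rests on the investigator judging it clinically relevant (Protocol 8.2.5), and the laboratory tables are the check that does not depend on that judgement.

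Four narrower replies also carry weight:
- The default rule does not name figures, so the maximum-value figures may use unscheduled central results. But a figure could then plot a participant whom the table omits.
- Protocol 10.2 expects a central sample alongside any local one. That limits the local-result loss to unpaired draws, which Protocol 4.1.2 foresees when central testing is not possible. A paired central sample taken off schedule is still unscheduled.
- Re-tests do replace an unavailable original.
- Visit 8a has its own column in the Schedule of Activities, so a programmer might treat it as scheduled. The footnote says otherwise, and off-schedule follow-up would be excluded on either reading.

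A reader might also infer that the loss falls mainly on whichever arm has more liver events, because that arm has more repeat draws. Step 4 shows why this does not follow: many repeats belong to participants already counted.

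**Conclusion.** The gap is real but limited to the laboratory-based liver tables. By default, and not by any liver-specific instruction, Visit 8a, off-schedule follow-up and re-tests with an available original do not count in the PDILI summary, the elevated liver test table or the Hy's Law laboratory table. Local results are removed from tables and figures outright. Any effect on the counts of participants meeting a threshold is downward. AESI, serious adverse event and MedDRA-query counts are unaffected, as is the elevated-liver listing, and no collected data are lost.

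The size is unknown. It is tempting to take 47% versus 93% as the undercount, but that is one row of an assumed range in which the loss disappears once excursions last 60 days. It also supposes that every participant had a Visit 8a. Amendment 5 is dated 30 June 2023, so participants already past Day 150 when it took effect would not have had one, and the documents do not say how many did.

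**What to change.** In SAP 5.4.3.1 and 5.4.3.1.1, with a matching line in 6.1.6, state that the participant-level liver threshold tables (elevated liver tests, PDILI, potential Hy's Law) and the maximum post-baseline liver figures use every post-baseline result:
- scheduled results;
- unscheduled results, naming Visit 8a;
- re-tests, whether or not the original is available;
- local results, flagged and expressed as multiples of the local ULN, where no paired central result exists.

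By-visit means can stay restricted to scheduled central results. A Month 5 column in by-visit outputs is optional, since only later participants had that visit.

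The cost is a few sentences in a SAP amendment before database lock and minor programming, because the data are already collected and listed. The one small downside is that local results must be converted using local reference ranges.

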5.1.1 Date imputation

Partial dates may be imputed for the following reasons:

- Classification of adverse events (AEs) as treatment-emergent
- Classification of medications as prior or concomitant
- Calculation of duration of exposure
- Calculation of duration of AEs
- Calculation of Parkinson's disease duration
- Determining start/end date of ST

Imputed dates will not be shown in the listings; all dates will be displayed as reported in the database.

The following rules will be applied for partial AE and concomitant medication start dates when classifying as treatment-emergent or prior/concomitant and also for determining AE duration:

- If only the month and year are specified and the month and year of the first dose of IMP is not the same as the month and year of the start date then the 1st of the month will be used, or the date of Screening visit 1 if this is later (if the latter imputation results in an end date that is earlier than the start date, then the 1st of the month will be used).
- If only the month and year are specified and the month and year of the first dose of IMP is the same as the month and year of the start date, then the date of the first dose of IMP will be used. If this results in an imputed start date that is after the specified end date, then the 1st of the month will be used, or the date of Screening visit 1 if this is later (if the latter imputation results in an end date that is earlier than the start date, then the 1st of the month will be used).

- If only the year is specified, and the year of the first dose of IMP is not the same as the year of the start date then January 01 will be used.
- If only the year is specified, and the year of the first dose of IMP is the same as the year of the start date, then the date of the first dose of IMP will be used. If this results in an imputed start date that is after the specified end date, then January 01, or the date of Screening visit 1 if this is later will be used (if the latter imputation results in an end date that is earlier than the start date, then January 01 will be used). If the imputed date is the date of first dose of IMP then the event will be regarded as treatment-emergent or the medication as concomitant.
- If the start date is completely unknown, the start date will not be imputed.

The following rules will be applied to partial AE and concomitant medication stop dates when classifying as treatment-emergent or prior/concomitant:

- If only the month and year are specified, then the last day of the month will be used.
- If only the year is specified, then December 31 of the known year will be used.
- If the stop date is completely unknown, the stop date will not be imputed.

If the above imputation still leads to a missing AE date:

Table 5–1: Calculation rules for duration of adverse events

Data availability	Onset date/time	Outcome date/time	Calculation rules
Complete data	D1	D2	$\text{Duration} = D2 - D1 + 1$
Start date missing	--	D2	$\text{Duration} = D2 - D0 + 1$ For a study participant in the SS, D0 is the date of first administration of IMP and for study participants who were randomized and not dosed, or for screen failures, D0 is the date of Screening Visit 1.
End date missing	D1		If the stop date is missing, duration will not be calculated.

Rules for calculating duration of exposure (UCB0599 or placebo)

For partial study medication stop dates, the last day of the month will be used if only day is missing. If the start date is missing or more than just the day is missing for the medication stop date, exposure duration will not be calculated. If partial dates are recorded for date of first and last dose of study medication this should be queried prior to applying any imputation rules.

Rules for calculating duration of Parkinson's Disease

Partial date of diagnosis dates will be imputed with the 15th of the month if only day is missing, if both day and month are missing the date will be imputed with 30th June (ie, the middle of the year).

Rules for determining start/end date of ST

Partial ST initiation dates will be imputed with the 15th of the month (if only day is missing) for the purposes of analyzing ST data (determining when ST started for ICE handling, and for calculating LEDD). This imputation rule will also apply to partial ST end dates. If month and/or year is missing, no imputation will be performed. If partial ST dates are recorded, these should be queried prior to applying any imputation rules.

